## **7.0 Data and Specimen Banking**

N/A

## **8.0 Sharing of Results with Subjects\***

We will publish research results at the peer-reviewed journal and/or scientific conferences. After completion of the study, results may be shared to research subjects if they want.

## **9.0 Study Timelines\***

The duration of an individual subject's participation in the study is three months including follow-up phone assessments. The estimated date for the investigators to complete this study is 02/01/2023.

## **10.0 Inclusion and Exclusion Criteria\***

A maximum of 40 persons with early-stage Alzheimer's disease and related dementias (ADRD) will be enrolled. Participants who are 50 to 90 years old will be considered eligible if they (1) have early- stage ADRD, (2) have caregiver-reported chronic pain (average pain in the past 3 months  $\geq$  3 out of 10), (3) have a caregiver willing to participate in the study who sees the participant at least 10 hours/week, (4) can speak and read English, and (5) have no plans to change medication regimens during the trial. The diagnosis of early-stage ADRD will be verified by PI based on Mini-Mental Status Exam score (generally 16-23), the blind/telephone version of the Montreal Cognitive Assessment (MoCA, generally 16-26), or Clinical Dementia Rating scores (generally 0.5-1.0). We will assess the use of medications that can influence responses to tDCS (e.g., selective serotonin reuptake inhibitors, beta-blockers) and include them as covariates in our statistical models. Participants will be excluded if they have any concurrent medical conditions that could confound the interpretation of outcome measures, pose a safety risk for any of the assessment or tDCS procedures, or preclude the successful completion of the protocol. Specific exclusion criteria are: (1) history of brain surgery, brain tumor, seizure, stroke, or intracranial metal implantation, (2) alcohol/substance abuse, (3) severely diminished cognitive function (i.e., Mini-Mental Status Exam score  $\leq$  15), and (4) hospitalization within the preceding year for neuropsychiatric illness. Participants who do not have a device with internet access will be provided a smartphone to use during the study.

## **11.0 Vulnerable Populations**

N/A

## **12.0 Local Number of Subjects**

The number of subjects who are expected to be enrolled and screened is 24, and the number of subjects needed to complete the research procedures (i.e., numbers of subjects excluding screen failures.) is 20. The total number of subjects to be accrued locally is 20, since we completed data collection for 20 subjects at the University of Texas Health Science Center at Houston before PI ([name]) moved to Florida State University.

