randomized, sham-controlled, parallel group (1:1 for two groups) pilot clinical trial. The central hypothesis is that home-based, remotely supervised tDCS will decrease pain. This hypothesis will be tested by pursuing the following specific aims: evaluate the preliminary effects of home-based M1-SO applied tDCS on clinical pain in persons with early-stage ADRD (specific aim 1); evaluate the preliminary effects of home-based M1-SO applied tDCS on pain related cortical response in persons with early-stage ADRD (specific aim 2); and evaluate the feasibility and acceptability of home based M1-SO-applied tDCS for pain management in persons with early stage ADRD (specific aim 3). We will also obtain data, as an exploratory aim, to investigate whether tDCS reduces behavioral and psychological symptoms of dementia. The proposed study will directly investigate the effects of home-based, remotely supervised tDCS in 40 persons with ADRD using an experimenter- and participant-blinded, randomized, sham-controlled, parallel group (1:1 for two groups) pilot clinical trial. Caregivers will set up and administer home-based tDCS for persons with ADRD and must be present at each home-based session, and participants will be remotely supervised by trained research staff at each stimulation to ensure the use of proper technique. Primary outcome (clinical pain assessed by the MOBID-2) will be performed by the caregivers. Caregivers will be trained at the in-person baseline visit to use tDCS devices and to perform outcome measures. tDCS session will be not performed if the caregiver is not available, and it needs to be the same caregiver throughout the trial. The proposed research is significant because it is expected to provide valuable insight into an exciting new modality of nonpharmacological pain management that is easy, safe, and noninvasive with minimal side effects.

Participants will do remotely-supervised tDCS at their home or private room for 5 days under real time supervision by the research staff. Data will be collected by study staff across several points using equipment and resources available at [name] (PI's) laboratory at Florida State University (see Table below). The primary endpoint will be clinical pain (MOBID-2) collected after the final intervention session. Participants will visit Florida State University two times, and each visit will take approximately 2 hours.

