## **25.0 Resources Available**

This study, funded by NIH, was approved by the IRB at the University of Texas Health Science Center at Houston. On this R15 project, all the data will be collected at the [name] laboratory at FSU. Adequate equipment and resources are available in the [name] laboratory to carry out the procedures and accommodate the personnel described in this proposal.

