## Statistical Analysis Plan (SAP)

A standard randomized controlled design will be adopted in this study, and we will randomly assign 40 patients to either active tDCS or sham tDCS (20 per group). Our primary analysis will compare clinical pain changes from baseline to the final intervention session between the active tDCS and sham tDCS groups. We plan to conduct 2 hypothesis tests for the main outcomes (MOBID-2 and fNIRS at Day 5) at a family-wise significance level of  $\alpha = 0.025$  after Bonferroni correction. With the sample size 20 per group, we will be able to detect the expected effect size of 1.0 with 80% power at a significance level of 0.025.

All data will be analyzed using the intention-to-treat approach. All demographic and clinical variables will be summarized using descriptive statistics, such as mean  $\pm$  standard deviation or median (interquartile range) as appropriate for continuous variables and frequency and percentage for categorical variables. The distribution of all variables will be examined to check the validity of distribution assumptions before any analysis, using measures of central tendency and a visual inspection of histograms and quantile-quantile plots. If the assumption of normality is not met, nonparametric approaches will be employed. SAS 9.4 (SAS Institute, Cary, NC) will be used to perform the proposed statistical analyses.

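### Minor: the 40 analysed participants appear to pool 20 from Houston with 20 from FSU, and prespecifying a site term would be a cheap protection of precision

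*Protocol*

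**What the plan says.** Protocol section 12.0 plans 20 local completers and gives the reason: "since we completed data collection for 20 subjects at the University of Texas Health Science Center at Houston before PI" moved to Florida State University (FSU). Section 10.0 caps total enrolment at 40, and the SAP states "we will randomly assign 40 patients to either active tDCS or sham tDCS (20 per group").

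On the analysis, the SAP says: "Our primary analysis will compare clinical pain changes from baseline to the final intervention session between the active tDCS and sham tDCS groups". It plans "2 hypothesis tests for the main outcomes (MOBID-2 and fNIRS at Day 5"), each at 0.025, and claims 80% power for an effect size of 1.0.

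The only covariates named in either document are in protocol section 10.0: medications that may alter the response to tDCS are to be recorded, and the team will "include them as covariates in our statistical models". Neither document mentions site, cohort or period in the analysis, or says whether allocation was blocked or stratified.

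Two statements in section 6.0 bear on how large a site difference could be. On equipment: "Data will be collected by study staff across several points using equipment and resources available at" the investigator's FSU laboratory. On the caregiver, who also rates MOBID-2: "it needs to be the same caregiver throughout the trial".

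**The concern.** No sentence says outright that the Houston data enter the analysis, but 20 completed plus 20 to come equals the 40 in the SAP, and no other reading fits. The analysed set then has two halves that differ in institution, calendar period and catchment. A two-arm comparison without a site term leaves any difference between those halves in the error variance.

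What stays in the error depends on the outcome. For MOBID-2, analysed as change from baseline, a constant difference in level between sites cancels and only a site difference in change remains. For fNIRS, the SAP names the Day 5 time point without saying whether the outcome is the Day 5 value or the change. If it is the Day 5 value, a level difference between laboratories also remains, and the documents do not say whether the Houston scans used the same set-up.

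What is at stake is power in a trial of 20 per arm planned at 80% for a large effect. The choice should be made in advance, because adding site after seeing the results would be data-driven.

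**Working it through.** **Inputs from the documents.** 20 participants per site (protocol 12.0); 20 per arm, effect size 1.0, significance level 0.025, power 80% (SAP).

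**Assumptions.** Two-sided test; effect of 1.0 in within-site SD units; a site difference D in the same units, not given in the documents and therefore varied; allocation either unblocked or balanced 10/10 within site, both computed.

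**Step 1: reproduce the stated power.** The noncentrality is 1.0 × √(20/2) = 3.162. A two-sided t-test at 0.025 with 38 df gives 79.3%. The normal formula gives 2 × (2.241 + 0.842)² / 1.0² = 19.0, rounded up to 20 per arm. The plan's figure is reproduced.

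**Step 2: effect of omitting site.** With half the patients at each site, an additive difference D adds D²/4 to the outcome variance, so the standard error is multiplied by about √(1 + D²/4): 1.03 at D = 0.5, 1.08 at 0.8 and 1.12 at 1.0.

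**Step 3: power without and with a site term.** Simulation, 200,000 trials per setting, linear model with arm against arm + site:

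| D (SD) | Unblocked: without / with | Balanced: without / with |
|---|---|---|
| 0 | 79.0 / 77.6% | 79.3 / 79.2% |
| 0.5 | 76.4 / 77.9% | 77.3 / 79.4% |
| 0.8 | 72.4 / 78.0% | 73.7 / 79.2% |
| 1.0 | 68.6 / 77.9% | 70.2 / 79.1% |

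The gain is about 1.5 to 2 points at 0.5 SD, 6 at 0.8 SD and 9 at 1.0 SD. With two binary medication covariates in both models (assumed 30% use each), power is about 2.5 to 3.5 points lower but the gains are nearly the same.

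**Step 4: cost and break-even.** With D = 0, exact calculation gives 79.26% (38 df, no site term), 79.18% (37 df, balanced) and 77.98% (37 df, averaged over unblocked splits). The cost is 0.08 to 1.28 points; the simulations put the upper end at 1.4. The term breaks even at D of about 0.34 SD if unblocked and about 0.12 SD if balanced.

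**Step 5: bias and type I error.** The mean estimated effect was 1.00 in every setting. Type I error without the term was 0.0245 to 0.0260 if unblocked. If balanced, it fell below nominal as D grew: about 0.021 at 0.5 SD and 0.012 at 1.0 SD, against 0.025. In that case the estimate itself is no more variable, but its standard error is overstated, so the test is conservative.

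**Step 6: other SD convention.** If the 1.0 is in total SD units, it equals √(1 + D²/4) within-site SDs. Unadjusted power then stays at about 79 to 81% for D from 0 to 1.0. With a site term and balanced allocation, the noncentrality is 3.162 × √(1 + D²/4) on 37 df, giving 81.8%, 85.3% and 88.0% at D = 0.5, 0.8 and 1.0. The gain is of similar, slightly smaller size.

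**The case against.** The strongest case against is that the benefit rests on a site difference nobody has shown. For the primary outcome the mechanism is weak: change scores remove level differences, the same caregiver is required throughout, treatment is given at home, and one device and montage are described. A 0.5 to 1.0 SD site difference in five-day change has no support in the documents. If allocation was unblocked and sites differ by less than about 0.34 SD, the term slightly reduces power. All of this stands, and it is why the point is minor.

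The fNIRS route is more plausible but also uncertain. The Day 5 label covers both outcomes, and MOBID-2 is explicitly a change, so it may only name the time point. fNIRS is also measured at baseline, and section 6.0 describes a response to thermal stimuli with rest intervals, which already removes part of any laboratory offset. A raw Day 5 analysis is one possible reading, not the stated plan.

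A reader might infer more than the documents support:
- *That pooling biases the result or inflates type I error.* It does neither (step 5).
- *That the stated 80% power is wrong.* It is reproduced. It is eroded only if the effect size is in within-site SD units and sites differ; the SAP does not say which SD was used.
- *That chance imbalance of arms within site is a further harm.* If allocation was unblocked, the chance of a 12/8 or worse split is 34.3%, and a 12/8 split shifts the unadjusted estimate by (12 − 8)/20 × D = 0.2D, or 0.10 SD at D = 0.5, against a standard error of √(2/20) = 0.32 SD. This is already averaged into the unblocked figures and must not be counted twice.
- *That the protocol conceals a second site.* Section 25.0 says "On this R15 project, all the data will be collected at the" FSU laboratory, and section 26.0 marks multi-site research as not applicable, but these describe local, future conduct, and section 12.0 discloses the Houston participants.

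**Conclusion.** The point holds as a minor, inexpensive improvement. The analysis set very probably pools two sites and periods, and no site term is planned. Validity is not threatened; at worst the test loses precision or, with allocation balanced within site, becomes conservative. The term pays materially only if sites differ by well over 0.5 SD on the analysed scale, which is unknown, unlikely for MOBID-2 change and more conceivable for fNIRS. The case for including it is the asymmetry: at most about 1.4 points of power lost against about 6 to 9 recovered at 0.8 to 1.0 SD. These figures rest on a two-sided 0.025 level, an additive site difference and within-site SD units. They do not address a treatment effect that differs by site.

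**What to change.** Before unblinding, add one sentence to the SAP: the MOBID-2 change and the Day 5 fNIRS outcome will each be analysed with arm, site (Houston, FSU) and the medication covariates of protocol section 10.0 as fixed effects. Report arm counts by site.

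Useful in the same edit: say whether the fNIRS outcome is the Day 5 value or the change from baseline, and state outright that the Houston participants are included. As a wording matter only, bring protocol sections 19.0 and 24.0 to 26.0 into line with section 12.0.

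The cost is one degree of freedom. If sites do not differ, that is about 0.1 point of power with allocation balanced within site and up to about 1.4 points if unblocked. With unblocked allocation, a small net loss remains for site differences below about 0.34 SD. No new data, visits or participants are needed.

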## **13.0 Recruitment Methods**

Participants will be recruited in Leon County under the direction of the PI. We will advertise around local institutions and communities by advertisement study flyers. PI will

oversee participant screening and recruitment. We will share recruitment materials with potential study participants, and those patients who contact the study team for more information about the study will be approached by study investigators or trained study personnel for further determination of eligibility screening requirements and informed consent either in-person at a scheduled baseline visit. We will also recruit through the Institute for Successful Longevity participant registry, as well as contacting previous participants of [name] study who have consented to be contacted for future research studies. MMSE will be used to exclude people with severely diminished cognitive function (i.e., MMSE score  $\leq 15$ ), and we will get the consent from the subject whose MMSE score is above 15. In addition to the MMSE cutoff, to ensure participant understanding of the study procedures, participants will be required to accurately describe the purpose and requirements of their participation in the study following review of the informed consent form.

Subjects will receive up to \$240 in gift cards for completing the entire protocol, and they will receive partial payment if they do not complete the entire study. For each self-brain stimulation, subjects will receive \$30 and an additional \$30 for each visit to our testing center and \$10 for each follow-up phone assessments.

## **14.0 Withdrawal of Subjects**

Participation in this study is completely voluntary. All participants will be informed of the nature of the procedures and associated risks. Also, participants will be informed that they can withdraw from the study at any time by calling study team at [contact] and that this will have no adverse impact on the study or on their own future medical treatment.

## **15.0 Risks to Subjects**

tDCS. The PI has extensive experience with tDCS interventions. Participants will be instructed to inform the experimenter of any discomfort during tDCS. To minimize risk associated with tDCS, participants will be asked to report any discomfort, and the examiner will monitor participants throughout the stimulation sessions. All tDCS sessions will be remotely supervised by a trained experimenter. Participants may stop at any time. tDCS has not been shown to cause seizures nor lower the seizure threshold in animals. There are no reports of seizure induced by tDCS in human participants in the literature. However, this may not be true for epilepsy patients, whose seizure threshold rates are likely abnormal. Thus, history of seizure is an exclusionary criterion for our study.

Demographic and clinical survey questionnaires. The potential risk of the questionnaires involves participants' feelings of discomfort or unease when reading or responding to survey questions that are personal. Throughout each questionnaire, participants will be reminded that participation is completely voluntary, they can refuse to answer any question, and they can stop at any time. Breaks will be given if needed. Research staff who collect data will have previous training in the conduct of all survey questionnaires.

Functional near-infrared spectroscopy. Optical fibers will be secured to the participant's scalp using the cap's grommets. Although there is no designed measure that protects the participants from the risk of discomfort due to prolonged wearing of headgear, we will assess the participants' level of discomfort through direct question immediately after wearing the headgear and periodically during the experiment. Participants will be instructed that they can discontinue the procedure if they experience any discomfort or unpleasant effects.

Thermal stimulation. The primary potential risk of thermal stimulation involves burning of the skin; however, we will be using the Medoc TSA-II Neurosensory Analyzer to create thermal stimulation. The TSA-II is covered under FDA 510K #K922052, which mandated both hardware and software safety limits that prevent burning of the skin. The following precautions will be employed in the proposed study: 1) participants will be informed that they can withdraw their arm from the stimulator at any time; 2) the experimenter will continuously monitor stimulus temperature and can manually discontinue stimulation at any point; and 3) the stimulator has a built-in shut-down system to prevent the delivery of prolonged or high-intensity stimuli. Inconvenience to participants will be minimized by delivering brief stimuli that are below the individual's thermal pain tolerance level. These procedures will ensure maximum patient safety and comfort while allowing successful and reliable imaging of the brain.

## **16.0 Potential Benefits to Subjects\***

Brain Stimulation have been shown to reduce pain in some older adults. We cannot promise any benefits to participants in this research. However, this study will help us to understand whether self-brain stimulation will reduce pain in older adults with Alzheimer's Disease and Related Dementia, which might lead to better treatment for people with such condition.

## **17.0 Data Management\* and Confidentiality**

PI has substantial experience in the design and implementation of data management procedures that provide accurate recording and storage of data, participant confidentiality, and timely analysis. Based on our experience, we believe that the major data management and analysis needs for the proposed project can be met by using a high-end PC, equipped with SPSS and SAS for Windows and appropriate spreadsheet programs. All data files will be automatically backed up daily.

The data entry system will require a login identification and password to gain access to the data. Where appropriate, validation and range rules will be applied to the actual entry fields. Only the PI and designated research staff will be able to view the data in its raw state.

All data files will be automatically backed up daily. We will ensure data changes are documented and there is no deletion of entered data. Data will be accessible only by research team members via an encrypted and password-protected computer, and we will prevent unauthorized access to data.

Confidentiality will be protected by assigning each participant a number, which will be used in all data tabulation and subsequent publications. The list linking this number to the participant's identity will be maintained in a password-protected data file, accessible only by authorized research personnel associated with the human testing components of this project. The PI will oversee the compliance of the study, maintaining strict adherence to the requirements of the law, research protocols, and health information security. Only trained research team members designated in the IRB- approved study protocol will collect data. REDCap (<http://www.project-redcap.org>) will be used to capture and store participant data, accessible only by research team members via an encrypted and password-protected computer. All research data will be labeled using the participant's unique identifier. No name or other identifying information will be used on research data. All paper data (e.g., participant contact information, consent forms) will be placed in a locked file cabinet within 24 hours of their acquisition.

## **18.0 Provisions to Monitor the Data to Ensure the Safety of Subjects**

[name], the PI, will have the primary responsibility for monitoring study research staff, who will receive training on the study design, recruitment, and protocol prior to study initiation. The research staff will attend weekly meetings with the PI and monthly team meetings during data collection with the PI and co-investigators to discuss any study-related issues regarding recruitment and follow-up data collection. These meetings will be used to discuss experiences with the intervention participants, provide consultation, ascertain whether the research staff are following study protocols, evaluate and reinforce cultural competence, and identify any potential adverse events. [name], the study statistician, will coordinate data management and analysis.

The Safety Monitoring Committee (SMC), which was approved by NIH, will be responsible for overseeing activities related to implementing the clinical trial to ensure patient safety, conformance to the clinical protocol, overall performance of the trial components, and integrity of the data being collected. The SMC will meet prior to the start of enrollment and then annually to review study progress (e.g., recruitment, retention, and safety procedures) and participant safety concerns and as needed to adjudicate any adverse events. All meeting materials will be considered privileged by SMC members. The SMC will comprise 3 members with expertise in neuromodulation, statistics, and geriatric clinical research: [name], professor of psychiatry and behavioral sciences at Baylor College of Medicine; [name], associate professor and biostatistician at the UTHealth Cizik School of Nursing; and [name], Assistant Professor, Geriatric and Palliative Medicine, UTHealth McGovern Medical School. The SMC members are independent of the project. These members are appropriately qualified to review the scientific design and conduct of the study, to evaluate safety and risks to participants, to interpret data statistically, and to make recommendations concerning the continuation, modification, suspension, or termination of the study.

